**NOTE:**

The following hospitalizations are not considered SAEs in BMS clinical studies:

- a visit to the emergency room or other hospital department < 24 hours, that does not result in admission (unless considered an important medical or life-threatening event)
- elective surgery, planned prior to signing consent
- admissions as per protocol for a planned medical/surgical procedure
- routine health assessment requiring admission for baseline/trending of health status (eg, routine colonoscopy)
- medical/surgical admission other than to remedy ill health and planned prior to entry into the study. Appropriate documentation is required in these cases
- admission encountered for another life circumstance that carries no bearing on health status and requires no medical/surgical intervention (eg, lack of housing, economic inadequacy, caregiver respite, family circumstances, administrative reason)
- Admission for administration of anticancer therapy in the absence of any other SAEs (applies to oncology protocols)

### **6.1.1      *Serious Adverse Event Collection and Reporting***

Sections 5.6.1 and 5.6.2 in the BMS-936558 Nivolumab Investigator Brochure represent the Reference Safety Information to determine expectedness of serious adverse events for expedited reporting. Following the subject's written consent to participate in the study, all SAEs, whether related or not related to study drug, must be collected, including those thought to be associated with protocol-specified procedures. All SAEs must be collected that occur during the screening period and within 100 days of the last dose of nivolumab. If applicable, SAEs must be collected that relate to any later protocol-specified procedure (eg, a follow-up skin biopsy).

The investigator must report any SAE that occurs after these time periods and that is believed to be related to study drug or protocol-specified procedure.

An SAE report must be completed for any event where doubt exists regarding its seriousness.

If the investigator believes that an SAE is not related to study drug, but is potentially related to the conditions of the study (such as withdrawal of previous therapy or a complication of a study procedure), the relationship must be specified in the narrative section of the SAE Report Form.

SAEs, whether related or not related to study drug, and pregnancies must be reported to Sponsor or designee within 24 hours of awareness of the event. SAEs must be recorded on the SAE Report Form; pregnancies on a Pregnancy Surveillance Form (electronic or paper forms). The preferred method for SAE data reporting collection is through the eCRF. The paper SAE/pregnancy surveillance forms are only intended as a back-up option when the eCRF system

is not functioning. In this case, the paper forms are to be transmitted via email or confirmed facsimile (fax) transmission to:

**SAE Email Address:** Refer to Contact Information list.

**SAE Facsimile Number:** Refer to Contact Information list.

For studies capturing SAEs through electronic data capture (EDC), electronic submission is the required method for reporting. In the event the electronic system is unavailable for transmission, paper forms must be used and submitted immediately. When paper forms are used, the original paper forms are to remain on site.

**SAE Telephone Contact** (required for SAE and pregnancy reporting): Refer to Contact Information list.

If only limited information is initially available, follow-up reports are required. (Note: Follow-up SAE reports must include the same investigator term(s) initially reported.)

If an ongoing SAE changes in its intensity or relationship to study drug or if new information becomes available, the SAE report must be updated and submitted within 24 hours to Sponsor or designee using the same procedure used for transmitting the initial SAE report.

All SAEs must be followed to resolution or stabilization.

BMS will be reporting adverse events to regulatory authorities and ethics committees according to local applicable laws including European Directive 2001/20/EC and FDA Code of Federal Regulations 21 CFR Parts 312 and 320.

## **6.2 Nonserious Adverse Events**

A *nonserious adverse event* is an AE not classified as serious.

### **6.2.1 Nonserious Adverse Event Collection and Reporting**

The collection of nonserious AE information should begin at initiation of study drug. Nonserious AE information should also be collected from the start of a placebo lead-in period or other observational period intended to establish a baseline status for the subjects.

Nonserious AEs should be followed to resolution or stabilization, or reported as SAEs if they become serious (see [Section 6.1.1](#)). Follow-up is also required for nonserious AEs that cause interruption or discontinuation of study drug and for those present at the end of study treatment as appropriate. All identified nonserious AEs must be recorded and described on the nonserious AE page of the CRF (paper or electronic).

Completion of supplemental CRFs may be requested for AEs and/or laboratory abnormalities that are reported/identified during the course of the study.

All nonserious adverse events (not only those deemed to be treatment-related) should be collected continuously during the treatment period and for a minimum of 100 days following discontinuation of dosing.

### **6.3        Laboratory Test Result Abnormalities**

The following laboratory test result abnormalities should be captured on the nonserious AE CRF page or SAE Report Form electronic) as appropriate. Paper forms are only intended as a back-up option when the electronic system is not functioning.

- Any laboratory test result that is clinically significant or meets the definition of an SAE
- Any laboratory test result abnormality that required the subject to have study drug discontinued or interrupted
- Any laboratory test result abnormality that required the subject to receive specific corrective therapy

It is expected that wherever possible, the clinical rather than laboratory term would be used by the reporting investigator (eg, anemia versus low hemoglobin value).

### **6.4        Pregnancy**

If, following initiation of the study drug, it is subsequently discovered that a study subject is pregnant or may have been pregnant at the time of study exposure, including during at least 5 half-lives after product administration, the investigator must immediately notify the Sponsor or designee of this event and complete and forward a Pregnancy Surveillance Form to BMS Designee within 24 hours of awareness of the event and in accordance with SAE reporting procedures described in [Section 6.1.1](#).

In most cases, the study drug will be permanently discontinued in an appropriate manner (eg, dose tapering if necessary for subject safety). Please call the Sponsor or designee within 24 hours of awareness of the pregnancy.

The investigator must immediately notify the Sponsor or designee of this event and complete and forward a Pregnancy Surveillance Form to Sponsor or designee within 24 hours of awareness of the event and in accordance with SAE reporting procedures described in Section 6.1.1.

Follow-up information regarding the course of the pregnancy, including perinatal and neonatal outcome and, where applicable, offspring information must be reported on the Pregnancy Surveillance Form.

Any pregnancy that occurs in a female partner of a male study participant should be reported to Sponsor or designee. In order for BMS to collect any pregnancy surveillance information from the female partner, the female partner must sign an informed consent form for disclosure of this information. Information on this pregnancy will be collected on the Pregnancy Surveillance Form.

### **6.5        Overdose**

An overdose is defined as the accidental or intentional administration of any dose of a product that is considered both excessive and medically important. All occurrences of overdose must be reported as an SAE (see Section 6.1.1 for reporting details.).

## **6.6 Potential Drug Induced Liver Injury (DILI)**

Hepatotoxicity, such as transaminase elevations and hepatitis, has been identified as an important risk for nivolumab.

Wherever possible, timely confirmation of initial liver-related laboratory abnormalities should occur prior to the reporting of a potential DILI event. All occurrences of potential DILIs, meeting the defined criteria, must be reported as SAEs (see [Section 6.1.1](#) for reporting details).

Potential drug induced liver injury is defined as:

1. AT (ALT or AST) elevation  $> 3$  times upper limit of normal (ULN)  
AND
2. Total bilirubin  $> 2$  times ULN, without initial findings of cholestasis (elevated serum alkaline phosphatase),  
AND
3. No other immediately apparent possible causes of AT elevation and hyperbilirubinemia, including, but not limited to, viral hepatitis, pre-existing chronic or acute liver disease, or the administration of other drug(s) known to be hepatotoxic.

A hepatic AE management algorithm that has been established ([Appendix 3](#)) and applied across the nivolumab program remains appropriate for managing drug-induced liver injury (DILI) cases. The experience to date shows that hepatic AEs, including possible DILI cases, were manageable using the established management algorithm and thus do not meaningfully alter the benefit/risk of nivolumab in the advanced malignancy populations.

## **6.7 Other Safety Considerations**

Any significant worsening noted during interim or final physical examinations, electrocardiogram, x-ray filming, any other potential safety assessment required or not required by protocol should also be recorded as a nonserious or serious AE, as appropriate, and reported accordingly.

## **7 DATA MONITORING COMMITTEE AND OTHER EXTERNAL COMMITTEES**

A Steering Committee comprised of trial investigators, trial statisticians, and BMS physicians will be created to design the trial and govern the trial's conduct, scope, and execution. No DMC will be formed for this trial. The oncology therapeutic area of BMS has primary responsibility for overall design and conduct of the study. Decisions regarding the study protocol will be made by the sponsor upon consultation with the steering committee.

## **8 STATISTICAL CONSIDERATIONS**

**Overview:** This is a Phase 2 single-arm clinical trial that investigates nivolumab across multiple cancer types. At least 25 tumor types (groups) will be considered. If additional groups are identified in the course of the trial, they will be enrolled and will be included within the statistical analysis provided reasonable estimates of the control response rates can be identified. The trial is designed to estimate the underlying ORR of nivolumab in each tumor type ( $\pi_g$ ). Supporting secondary objectives include the duration of response, TTR, CBR, OS, and safety. All subjects will receive nivolumab.

A hierarchical model that borrows information across tumor subgroups will be used to strengthen the overall evidence within each subgroup. Using the hierarchical model, both continuous monitoring for futility and success will be undertaken throughout the study.

Regularly scheduled trial update analyses occur at most every 4 weeks. At each of these analyses, a Bayesian hierarchical model is fit across the data in all cohorts. For each cohort we determine the Bayesian posterior probability that the treatment effect in that cohort (treatment compared to historical control) is greater than 0 (eg, that treatment is better than control). Formally, if  $\theta_g$  is the true log odds treatment effect for cohort  $g$ , we compute  $Pr(\theta_g > 0 | \text{data})$  for each cohort  $g$ . At the regularly scheduled trial update analyses, each cohort may stop enrollment for success or futility. If a cohort stops enrollment, subjects currently in the cohort are all still followed to their primary endpoint.

Separate final analyses will be conducted for each cohort. A final analysis for a group will occur after enrollment in that group is complete and after all subjects in that group have at least 28 weeks follow-up. Once a group is stopped early for futility, the group will not be re-opened for further enrollment. The final analysis for a cohort declares success if the Bayesian posterior probability that the treatment effect in that cohort (treatment compared to historical control) is above 80%. For example, cohort  $g$  will be declared a success at cohort  $g$ 's final analysis if  $Pr(\theta_g > 0 | \text{data}) > 0.80$ . This posterior probability will incorporate the entire dataset at the time of analysis through the Bayesian Hierarchical Model.

**Statistical Hypotheses:** Let  $Y_i$  be the response indicator for the  $i$ th subject. Define  $\pi_g = Pr(Y_i = 1 | g_i = g)$  as the underlying probability of response for group  $g$  for the experimental treatment and  $R_g$  as the assumed probability of response for group  $g$  within the (historical) control population. Transformation to the logit scale is applied for modeling purposes. Let  $\theta_g$  be the mean log odds treatment effect, ie,

$$\theta_g = \log(\pi_g/(1-\pi_g)) - \log(R_g/(1-R_g)).$$

Thus,  $\theta_g$  is the logistic regression coefficient for the treatment within tumor group  $g$ . The primary analysis is a set of group specific tests of  $\theta_g > 0$  (equivalently,  $\pi_g > R_g$ ) meaning that the treatment is better than the assumed control rate within that group. Thus, the following hypotheses are tested for each tumor group  $g$ :

$$H0g : \theta_g \leq 0,$$

$$H1g : \theta_g > 0.$$

The assumed control ORRs ( $R_g$ ) vary by group and are provided in the Table 8-1 below.

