**Study Drug: includes Investigational [Medicinal] Products (IP/IMP) as listed:**

Study Drug for CA209627		
Medication	Potency	IP/Non-IP
Nivolumab BMS936558-01	40 mg/4 mL and 100 mg/10 mL solution in a single-dose vial.	IP

**Study Assessments:** The primary endpoint of this trial is investigator-assessed ORR of nivolumab monotherapy which is based on tumor assessments at baseline and then at 28 weeks from first dose of nivolumab. Clinical benefit will be defined. Tumor assessments will occur at week 8, week 16, week 28, and then every 12 weeks until disease progression, regardless of any dose delays. Adverse events will be assessed continuously during the study and for 100 days after last trial dose of nivolumab.

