### **5.3.1      *Imaging Assessment for the Study***

Images will be collected centrally and may be reviewed by blinded independent central review (BICR) at a later date, or at any time during the study. Image acquisition guidelines and submission process will be outlined in the CA209-627 Imaging Manual to be provided by the core lab.

Any additional imaging that may demonstrate tumor response or progression (including scans performed at unscheduled timepoints and/or at an outside institution) should be collected for RECIST 1.1 tumor assessment and submitted to the BICR.

Study evaluations will take place in accordance with [Table 5.1-1](#), [Table 5.1-2](#), [Table 5.1-3](#), and [Table 5.1-4](#) according to RECIST 1.1. CT with IV contrast are the preferred imaging modalities for assessing radiographic tumor response. In cases where contrast is contraindicated, a non-contrast scan will suffice. Screening (baseline) tumor assessments of, chest, abdomen, pelvis, and all known / suspected sites of disease are to be performed prior to first dose. Subsequent assessments should include chest, abdomen, pelvis, and all known / suspected sites of disease using the same imaging method and technique as was used at baseline.

For evaluating CNS metastasis, brain MRI is the required imaging method, and assessment is required during screening in subjects with a known history of treated brain metastases. All known sites of disease (including CNS) should be assessed at baseline and subsequent assessments using the same imaging method and technique. If more than 1 method is used at screening, then the most accurate method according to RECIST 1.1 should be used when recording data, and should again be used for all subsequent assessments. Bone scan, PET scan, or ultrasound is not adequate for assessment of RECIST 1.1 response. Previously treated CNS metastases are not considered measurable lesions for purposes of RECIST 1.1 determined response. Subjects with a history of brain metastasis should have surveillance MRI approximately every 12 weeks or sooner if clinically indicated.

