### **8.5           Interim Analyses**

**Interim Monitoring** will be conducted, at most, every 4 weeks. At each analysis, the groups will be evaluated for futility and success by comparing posterior quantities for the overall response rate to pre-specified early stopping criteria based on the hierarchical model based on population of subjects with at least 28 weeks of follow-up. The design may limit the maximum number of subjects per group to 25 subjects within the trial. Available resources will be used more effectively by enrolling subjects in groups that offer greater promise of efficacy. Internal assessment of the program will also take into consideration for the final decision of early stopping.

**Early Futility:** If there is a sufficiently low probability (20%) that the ORR in a group exceeds the historical rate  $R_g$  by at least 10%, then the group will stop enrollment early for futility. Formally, enrollment will stop early for futility if:

$$Pr(\pi_g > R_g + 0.10) < 0.20$$

A group is only eligible for early stopping for futility once a minimum of 5 subjects have been evaluated for ORR in that group.

**Early Success:** If there is a sufficiently high probability (95%) that the ORR in a group exceeds the historical rate  $R_g$ , then the group may stop enrollment early for success. Formally, enrollment may stop early for success if:

$$Pr(\pi_g > R_g) > 0.95$$

A group is only eligible for early stopping for success once a minimum of eligible 8 subjects have been evaluated for ORR in that group.

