### 1.11.3 Confirmation of Scans and External Evaluation

- Verification of Response:** Confirmation of response (CR or PR) is required. Confirmed CR or PR will be claimed only if the criteria for each are met at a subsequent timepoint (minimum 4 weeks after criteria for an objective response are first met).
- Verification of Progression:** Progression of disease should be verified in cases where progression is equivocal. If repeat scans confirm PD, then progression should be declared using the date of the initial scan. If repeat scans do not confirm PD, then the subject is considered not to have progressive disease per RECIST 1.1.
- External Evaluation of scans:** For all subjects, BMS will request the transfer of anonymized scans for a BMS internal or external evaluation through a third party. For tumor types where data from study CA209-032 will potentially be used for future NDA submissions, BMS will request the transfer of anonymized scans from all subjects with this tumor type for a BMS internal or external evaluation through a third party.

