### 1.12 Best overall response: All time points

The best overall response is determined once all the data for the subject is known. It is defined as the best response designation, as determined by the investigator, recorded between the date of first treatment and the date of objectively documented progression per RECIST 1.1 or the date of subsequent therapy, whichever occurs first. For subjects without documented progression or subsequent therapy, all available response designations will contribute to the BOR assessment. The subject's best overall response assignment will depend on the findings of both target and non-target disease and will also take into consideration the appearance of new lesions.

Complete or partial responses may be claimed only if the criteria for each are met at a subsequent time point (minimum 4 weeks after criteria of objective response are first met). In this circumstance, the best overall response can be interpreted as in Table 4.

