4 ENDPOINTS

4.1 Primary Endpoint(s)

The primary endpoint of this trial is investigator-assessed ORR of nivolumab monotherapy. ORR is defined as the number of participants with a best overall response of confirmed CR or PR divided by the number of all treated participants. Best overall response is defined as the best response designation, as determined by investigator, recorded between the date of first dose and the date of objectively documented progression per tumor-specific response criteria or the date of subsequent therapy, whichever occurs first. For participants without documented progression or subsequent therapy, all available response designations will contribute to the BOR determination. For subjects who continue treatment beyond progression, the BOR will be determined based on response assessments up to the time of initial RECIST 1.1 progression.

Tumor assessments will occur at Week 8, Week 16, Week 28 and then every 12 weeks until disease progression. BOR for each patient will be derived as one of the following categories:

- Complete response (CR): At least two objective statuses of CR documented with a minimum of 4 weeks apart before progression.
- Partial response (PR): At least one objective status of PR at one visit and then at the subsequent (not need to be second one, any visits after the first 'PR') visit with a CR or PR, and two objective statuses documented with a minimum of 4 weeks apart before progression.
- Stable disease (SD): At least one objective status of stable documented at least 6 weeks after first dosing date and before progression but not qualifying as CR, PR, Or for unconfirmed CR or PR documented at least 6 weeks after first dosing date and before progression.
- Progressive Disease (PD): Objective status of progression and not qualifying as CR, PR or SD.
- Not evaluable (NE).

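### A response first seen at the Week 28 scan counts as a non-response at a 28-week analysis because confirmation is not yet due, and at an early futility look this can close a cohort permanently.

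*Protocol*

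**What the plan says.** **Endpoint.** Protocol Section 8.3.1 and SAP Section 4.1 define ORR as confirmed CR or PR over all treated subjects. Protocol Appendix 4, Section 1.11.3 adds: "Confirmed CR or PR will be claimed only if the criteria for each are met at a subsequent timepoint", with a minimum gap of 4 weeks.

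**Scans.** The synopsis states: "Tumor assessments will occur at week 8, week 16, week 28, and then every 12 weeks until disease progression". The scheduled scan after Week 28 is therefore Week 40.

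**Who is analysed, and when.** Protocol Section 8.5 evaluates cohorts "based on the hierarchical model based on population of subjects with at least 28 weeks of follow-up". SAP Section 6.3 requires only that 28 weeks have elapsed since first dose. A cohort's final analysis may run "after all subjects in that group have at least 28 weeks follow-up" (Protocol Section 8). SAP Section 7.5.2.2 sets the study's final analysis at least 28 weeks after the last subject's first treatment.

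**Unconfirmed responses.** The stable disease category in SAP Section 4.1 includes this clause: "Or for unconfirmed CR or PR documented at least 6 weeks after first dosing date and before progression". Table 4 of Appendix 4 gives stable disease or not evaluable when a response is followed by a non-evaluable timepoint. Both are non-responses for ORR.

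**Futility.** Enrolment stops if Pr(π_g > R_g + 0.10) < 0.20, from 5 evaluated subjects (Protocol Section 8.5, SAP Section 7.5.2.3). A cohort closed for futility is not re-opened, but its enrolled subjects are still followed to the primary endpoint (Protocol Section 8).

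**The concern.** A subject whose first response appears at Week 28 has not failed confirmation; it is simply not yet due. At a 28-week cut that subject still counts as a non-responder, exactly like one whose response was lost at the next scan. This sits poorly with Appendix 4, Section 1.12: "The best overall response is determined once all the data for the subject is known".

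At a final analysis the effect is a slightly low ORR. At a futility look with about five subjects, a single pending response can decide whether the cohort closes. Later confirmation can still count at that cohort's final analysis, but it cannot restore the enrolment that was lost. No visible text asks anyone to look at pending responses before closing.

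**Working it through.** **The plan's own figures.** Protocol Section 8.1 gives per-group power of 86.8% to 98.0% at an odds ratio of 3 and per-group type I error of 2.1% to 9.5%. They come from the hierarchical model simulated in Appendix 1. Its priors, borrowing and accrual are not in the visible text, so these figures can be neither reproduced nor challenged. What follows uses a simpler stand-in and shows direction and rough size only.

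**Timing.** Earliest confirmation of a Week 28 response is 28 + 4 = Week 32, by an unscheduled scan. On schedule it is 28 + 12 = Week 40. With looks every 4 weeks, 12/4 = 3 looks can fall in the gap. Responses first seen at Week 8 or 16 can be confirmed by the Week 28 scan.

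**Can one response decide closure?** Assume one cohort alone, R_g = 10%, and compute the posterior tail above R_g + 0.10 = 0.20.

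| Prior | Data | Pr(π > 0.20) | Decision at 0.20 |
|---|---|---|---|
| Jeffreys | 0/5 | 0.125 | stop |
| Jeffreys | 1/5 | 0.549 | continue |
| Uniform | 0/5 | 0.8^6 = 0.262 | continue |
| Uniform | 0/7 | 0.8^8 = 0.168 | stop |
| Uniform | 1/7 | 0.8^8 + 8 × 0.2 × 0.8^7 = 0.503 | continue |

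Under Jeffreys, one response decides the matter at n = 5 for R_g from 5% to 20%: 0/5 gives 0.191 down to 0.053, and 1/5 gives 0.673 down to 0.337. Under the uniform prior and R_g = 10%, the flip comes at 7 subjects.

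**How often?** Assumptions:
- True ORR is 25%, which is odds ratio 3 at R_g = 10%: odds 3 × 1/9 = 1/3.
- A share q of 10% to 20% of responses is first seen at Week 28. The documents give no figure.
- There is no unscheduled confirmatory scan.
- Dosing is evenly spaced over 24 months (104 weeks, Protocol Section 3.1).

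A subject at 40 weeks or more shows a response with probability 0.25. A subject under 40 weeks shows one with probability 0.25(1 − q), that is 0.225 or 0.20.

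*Case A, 14 subjects (350/25), spacing 104/13 = 8.0 weeks.* Subject 5 reaches 28 weeks at week 60. The five ages are 60, 52, 44, 36 and 28 weeks, so 2 of 5 are under 40.
- P(0/5) with nothing pending: 0.75^5 = 23.7%.
- With late responses: 0.75^3 × 0.775^2 = 25.3%, to 0.75^3 × 0.80^2 = 27.0%.

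*Case B, 25 subjects (the group cap), spacing 104/24 = 4.33 weeks.* The first look is at week 45.3, and 3 of 5 are under 40 weeks.
- With late responses: 0.75^2 × 0.775^3 = 26.2%, to 0.75^2 × 0.80^3 = 28.8%.

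For 0/7, where the uniform prior flips, the chance is 14.3% to 15.2% (A) or 14.7% to 16.2% (B), against 13.3%. At this accrual at most 4 (A) or 7 (B) subjects are under 28 weeks at once, so the 12-subject pause rule does not intervene.

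**Repeated looks.** Two separately programmed simulations of one cohort used 4-weekly looks, no borrowing, the Jeffreys prior and q = 20%. Counting pending responses as responders before closing changed false futility closures as follows:

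| | N = 14 | N = 25 |
|---|---|---|
| First simulation | 26.9% to 23.3% | 37.5% to 32.3% |
| Second simulation | 34.5% to 31.2% | 38.7% to 33.3% |

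The levels depend on conventions that the documents do not settle. The reduction is 3.3 to 5.4 points throughout, with little added continuation of ineffective groups. In the first simulation final success moved only from 63.6% to 64.6% (N = 14) and from 76.6% to 77.2% (N = 25).

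**Final analysis.** The cut is the day the last subject reaches 28 weeks. Success needs a Jeffreys posterior above 0.80, that is at least 3/14 or 4/25. The two binomials are convolved exactly.

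| | Under 40 weeks | Power, none pending | q = 10% | q = 20% |
|---|---|---|---|---|
| A | 2 of 14 | 71.9% | 70.9% | 69.8% |
| B | 3 of 25 | 90.4% | 89.8% | 89.2% |

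Type I error in case A moves from 15.8% to between 15.3% and 14.9%. No interim stopping is applied here.

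**The case against.** A reader might infer that the plan has no rule for unconfirmed responses. It has one: SAP Section 4.1 and Table 4 of Appendix 4 make them non-responses. What is missing is narrower, a distinction between pending and failed confirmation.

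The 28-week entry point also looks deliberate. SAP Section 7.5.2.3 frames it as the opportunity to complete 28 weeks of follow-up, which leaves room to confirm responses first seen at Weeks 8 and 16. At the final analysis 28 weeks is a minimum, so a later cut needs no amendment. Extra imaging, "including scans performed at unscheduled timepoints and/or at an outside institution", is collected and can confirm a response early. On stopping, Protocol Section 8.5 adds: "Internal assessment of the program will also take into consideration for the final decision of early stopping". Appendix 1 and the section on the rationale for 28-week assessments are not visible and may deal with pending data.

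The size is modest too. Most 0/5 results would occur with nothing pending (23.7/28.8 = 82% to 23.7/25.3 = 94%). The stand-in ignores borrowing, and its 15.8% type I error is well above the plan's 2.1% to 9.5%, so it is not the trial's model.

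All of this stands, and it makes the point minor. It does not remove it: internal assessment is discretionary, nothing visible directs it to pending responses, and continued follow-up does not reopen enrolment.

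**Conclusion.** The point holds as a minor one. At any trial update or final analysis that includes subjects with only 28 weeks elapsed, a response first seen at Week 28 is scored as stable disease unless an early scan has confirmed it, and the visible text does not separate pending from failed confirmation.

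The direction is conservative: apparent ORR, power and type I error all fall. At the final analysis the loss is about 0.6 to 2 points of power in the illustration. At early futility looks one pending response can reverse the decision, depending on the prior, and rechecking would avoid roughly 3 to 5 points of false closures under the Jeffreys prior with q = 20%. The main loss there is enrolment.

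These sizes rest on an assumed late-response share, even accrual and no borrowing. The documents do not support reading this as an error in the stated power or type I error, or as a material bias in the final success decisions.

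**What to change.** 1. In Protocol Section 8.5 and SAP Section 7.5.2.3, add a step before a futility closure takes effect: list responses awaiting confirmation and rerun Pr(π_g > R_g + 0.10) < 0.20 counting them as responders. If the decision changes, defer permanent closure until they are settled. Leave the success rule unchanged.
2. At each cohort's final analysis, keep the confirmed count as primary and add a sensitivity result counting pending responses. Alternatively, set a cut that does not depend on outcome: every subject has had the opportunity for the scan after Week 28, or has best overall response otherwise settled. Do not delay only when a response is pending, since follow-up would then depend on outcome in the favourable direction.
3. If Appendix 1 already covers this, a cross-reference in those sections is enough.

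**Cost.** A small extra analysis at updates where closure is indicated, an occasional deferral of up to about 12 weeks, possibly a few more subjects within the existing caps, and a check that the simulated operating characteristics in Protocol Section 8.1 still hold. The futility recheck and the sensitivity result need no added scans.
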